Data Analysis for Drug Repurposing for Effective Alzheimer's Medicines – Propranolol/Carvedilol vs Atenolol/Bisoprolol/Sotalol

NCT05794997

July 7, 2023

1. Comparison Details

a. Intended aim(s)

To evaluate the comparative risk of dementia onset between patients treated with Propranolol or Carvedilol versus Atenolol, Bisoprolol, Sotalol for hypertension.

b. Primary endpoint

Incident dementia (i.e., Alzheimer's disease, vascular dementia, senile, presenile, or unspecified dementia, or dementia in other diseases classified elsewhere).

2. Person responsible for implementation of replication in Action

[name]

3. Data Source(s)

Medicare, 2008-2019

4. Study Design Diagrams

[figure not shown]
[figure not shown]

Figure- Alternate analysis approaches

■■■ Included person-time
■■■ Excluded person-time

5. Cohort Identification

a. Cohort Summary

This study will employ a new user, active comparator, observational cohort study design comparing Propranolol or Carvedilol to hydrochlorothiazide. The patients will be required to have continuous enrollment during the baseline period of 365 days before initiation of Propranolol or Carvedilol or Atenolol, Bisoprolol or Sotalol (index date). Follow-up for the outcome (dementia) differs between analyses. Follow-up begins the day after drug initiation (analysis 1, 3, 4); 180 days after drug initiation (analysis 2).

b. Key details regarding cohort creation

Index date:

- Day of initiation of new Propranolol or Carvedilol or Atenolol, Bisoprolol or Sotalol use

Inclusion criteria for analyses 1, 3, 4:

- Aged \geq 65 years on the index date
- 365 days enrollment in Medicare Parts A, B, and D with no HMO coverage
- No use of Propranolol, Carvedilol, Atenolol, Bisoprolol, Sotalol any time prior to index date (all available lookback approach with a minimum of 365 days)
- No use of Propranolol, Carvedilol and Atenolol, Bisoprolol, Sotalol concomitantly on index date
- No diagnosis of dementia any time prior to and including index date
- At least 1 inpatient claim or 2 outpatient claims with hypertension diagnosis recorded in 365 days prior to index date

Inclusion criteria for analysis 2:

- Aged \geq 65 years on the index date
- 365 days enrollment in Medicare Parts A, B, and D with no HMO coverage
- No use of Propranolol, Carvedilol, Atenolol, Bisoprolol, Sotalol any time prior to index date (all available lookback approach with a minimum of 365 days)

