Anti-epileptic mood stabilizers	Lipid lowering drugs
Anti-epileptics (other than mood stabilizers)	Non-insulin diabetes medications
Atypical antipsychotics	Insulin
Benzodiazepines	Antidepressants
Serotonin-norepinephrine reuptake Inhibitors	Typical antipsychotics
Selective serotonin reuptake inhibitors	Anticoagulants
Tricyclic antidepressants (TCAs)	Antiplatelet agents

Comorbid conditions	
Atrial fibrillation	Chronic liver disease
Coronary artery disease	Asthma
Heart failure	Ischemic heart disease
Stroke or transient ischemic attack	Chronic obstructive pulmonary disease
Peripheral vascular disease	Malignancy
Hyperlipidemia	Drug or alcohol abuse or dependence
Renal dysfunction	Venous thromboembolism

ICD-9, ICD-10, HCPCS, and NDC codes used to define the covariates listed above are available in Appendix A.

c. Outcome variables and study follow-up:

- **Primary outcome:** incident dementia, i.e., Alzheimer's disease, vascular dementia, senile, presenile, or unspecified dementia, or dementia in other diseases classified elsewhere. Outcome will be defined by 1 inpatient claim or 2 outpatient claims in analysis 1, 2, 3. In analysis 4, the outcome will be defined by 1 inpatient or 1 outpatient claims and 1 prescription claim for a symptomatic treatment [donepezil, galantamine, rivastigmine, and memantine] within 6 months of each other with outcome date assigned to second event in the sequence.

- Secondary outcomes: Individual component:
Alzheimer's disease

Condition	ICD-9 and ICD-10 codes
Alzheimer's disease	331.0*, F00*, G30*
Vascular dementia	290.4*, F01*
Senile, presenile, or unspecified dementia	290.0*, 290.1*. 290.3*, 797*, F03*
Dementia in other diseases classified elsewhere	331.1*, 331.2*, 331.7*, 294.1*, F02*

For analysis 1,3, and 4 the follow-up will start the day after initiation of Propranolol or Carvedilol and Atenolol, Bisoprolol or Sotalol and will continue until the earliest date of the following events:

- The first occurrence of the outcome of interest
- The date of end of continuous registration in the database,
- End of the study period,
- Measured death event occurs,
- The date of drug discontinuation, defined as the date of the last continuous treatment episode of the index drug (Propranolol or Carvedilol and hydrochlorothiazide) plus a defined grace period (i.e., 90 days after the end of the last prescription's days' supply in main analyses).

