For analysis 2, the follow-up will start 180 days after initiation of Propranolol or Carvedilol and Atenolol, Bisoprolol or Sotalol and will continue until the earliest date of the following events:

- The first occurrence of the outcome of interest, unless otherwise specified for selected outcomes,
- The date of end of continuous registration in the database,
- End of the study period,
- Measured death event occurs,
- Maximum allowed follow-up time (1095 days) reached

7. Propensity score analysis

We will use a propensity-score (PS)¹-based approach to account for measured confounding in this study. The PS will be calculated as the predicted probability of initiating the exposure of interest (i.e., the repurposing candidate) versus the reference drug conditional on baseline covariates using multivariable logistic regression constructed separately in each data source. On average, patients with similar PSs have similar distribution of potential confounders used to estimate the PS. Therefore, analyses conditioned on the PS provide effect estimates that are free from measured confounding. For all our analyses, initiators of each exposure of interest will be matched with initiators of the reference exposure based on their PS within each data source.² Pair matching will be conducted using a nearest-neighbor algorithm, which seeks to minimize the distance between propensity scores in each pair of treated and reference patients,³ and a caliper of 0.025 on the natural scale of the PS will be used to ensure similarity between the matched patients.⁴

We report multiple diagnostics for PS analysis in this protocol. First, the PS distributional overlap is provided between two groups before and after matching to ensure comparability of these groups.⁵ Next, balance in each individual covariate between two treatment groups is reported using standardized differences.⁶

8. Table for covariate balance

Variable	Crude			PS-Matched		
	Propranolol and Carvedilol (N = 583,870)	Atenolol, Bisoprolol, Sotalol (N = 233,467)	St. Diff	Propranolol and Carvedilol (N = 222,015)	Atenolol, Bisoprolol, Sotalol (N = 222,015)	St. Diff
Demographics						
Age, mean (SD)	75.02 (7.00)	74.75 (6.77)	0.04	74.77 (6.82)	74.75 (6.78)	0.00
Gender, n (%)						
Male	281,232 (48.2%)	97,628 (41.8%)	0.13	93,749 (42.2%)	94,142 (42.4%)	0.00
Female	302,638 (51.8%)	135,839 (58.2%)	-0.13	128,266 (57.8%)	127,873 (57.6%)	0.00
Race, n (%)						

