Peripheral vascular disease	129,600 (22.2%)	40,710 (17.4%)	0.12	39,670 (17.9%)	39,327 (17.7%)	0.01
Renal dysfunction	236,212 (40.5%)	56,863 (24.4%)	0.35	56,068 (25.3%)	56,128 (25.3%)	0.00
Stroke or transient ischemic attack	68,173 (11.7%)	23,278 (10.0%)	0.05	22,586 (10.2%)	22,216 (10.0%)	0.01
Venous thromboembolism	37,549 (6.4%)	11,617 (5.0%)	0.06	11,391 (5.1%)	11,122 (5.0%)	0.00

9. Statistical analysis plans

Incidence rates for the outcome will be estimated for the treatment and reference groups before and after PS matching. The competing risk of death could be of concern for the current set of analyses if mortality is frequent among patients included in the cohort and if differences in the risk of mortality between treatment and reference groups are substantial. In the PS-matched sample, we will use cause-specific hazard models⁷ to provide hazard ratios averaged over the entire follow-up period as well as interval specific hazard ratios (1, 2, and 3 years) for the association between the treatment of interest and risk of ADRD after considering all-cause mortality as a competing event. Pre-specified subgroup analyses will be conducted based on age, sex, and baseline cardiovascular disease. In addition to the Medicare dataset, we will pursue a similar analysis within Clinical Practice Research Datalink (CPRD), a UK population health dataset, to validate our results.

10. References

4. Austin PC. Some Methods of Propensity-Score Matching had Superior Performance to Others: Results of an Empirical Investigation and Monte Carlo simulations. *Biometrical Journal*. 2009;51(1):171-184.

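### Analyses 1, 3 and 4 do not end follow-up when a patient starts a drug of the other group, so some comparator and dual-use time counts to the first drug

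*Combined protocol and SAP*

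**What the plan says.** Section 6c of the combined protocol and SAP states that follow-up in analyses 1, 3 and 4 "will continue until the earliest date of the following events" and then lists five: the outcome, end of continuous registration, end of the study period, death, and discontinuation. Only the last concerns treatment. It is given as "The date of drug discontinuation, defined as the date of the last continuous treatment episode of the index drug", followed by the drug names and the grace period: "Propranolol or Carvedilol and hydrochlorothiazide) plus a defined grace period". In the main analyses the grace period is "90 days after the end of the last" prescription's days' supply.

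The only rule on joint use of the two groups is an entry criterion in Section 5b: "No use of Propranolol, Carvedilol and Atenolol, Bisoprolol, Sotalol concomitantly on index date". Section 9 says of the matched sample that "we will use cause-specific hazard models", and mentions neither switching, add-on use nor time-varying exposure. Section 7 on the propensity score does not mention them either.

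Analysis 2 is different. Its list has no discontinuation event and ends instead with "Maximum allowed follow-up time (1095 days) reached".

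**The concern.** Because analyses 1, 3 and 4 stop at discontinuation, they aim at risk while on the assigned drug group. For that aim, the start of a drug from the opposite group is a natural end point, and it is missing from the list. Both groups are beta-blockers given to patients with hypertension, so some crossover is plausible.

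Two cases follow from the text:

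- **Clean switch.** A patient moves from, say, carvedilol to bisoprolol. The index drug runs out, and follow-up ends up to 90 days later. Until then, time and events on bisoprolol count to carvedilol.
- **Add-on.** The patient keeps the index drug and adds one from the other group. The add-on does not end follow-up, and dual-use time counts to the index drug until one of the five listed events occurs.

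The contrast between the groups is diluted in both cases. A dementia event soon after a switch is also assigned to the drug that was stopped.

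The same sentence has a second problem. It identifies the index drugs as "Propranolol or Carvedilol and hydrochlorothiazide", so read literally it defines no treatment episode for atenolol, bisoprolol or sotalol. It also leaves open whether a move within a group, such as propranolol to carvedilol, ends the episode. Two programmers could build different follow-up times from it.

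**Working it through.** The plan states no figure on this point, so there is none to reproduce. The check is a comparison of the text followed by an illustration under stated assumptions.

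**Text.** Every place where a switch rule could stand was read:

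| Place | Rule on starting the other group |
|---|---|
| Section 5b, eligibility | Index date only |
| Section 6c, analyses 1, 3, 4 | Five stopping events, none of them this |
| Section 6c, analysis 2 | No treatment-related stopping event |
| Section 7, propensity score | None |
| Section 9, analysis | None |
| Section 4, design figures | Not shown in the text available |

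**Inputs for the size.** The 90-day grace period (about 0.25 year) is from Section 6c. The rest are assumptions, because the documents do not give them: share switching s = 5–15% in each group, mean time on drug T = 0.75–1.5 years, true hazard ratio h = 0.80, constant hazards, and the same contamination in both groups.

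**Share of person-time misallocated by the 90-day tail:** m = s × 0.25 / (T + 0.25)

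- Low end: 0.05 × 0.25 / (1.5 + 0.25) = 0.0125 / 1.75 = 0.7%.
- High end: 0.15 × 0.25 / (0.75 + 0.25) = 0.0375 / 1.00 = 3.75%.

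**Hazard ratio observed when both groups are contaminated:** [(1 − m)h + m] / [(1 − m) + mh]

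- m = 0.00714: 0.8014 / 0.9986 = 0.803.
- m = 0.0375: 0.8075 / 0.9925 = 0.814.

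Both groups must be contaminated in the formula because the stopping rule is the same for both.

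**Other assumptions.** Taking 5–20% switching and mean counted follow-up of 365–730 days, m = s × 90 / (days of follow-up). This runs from 0.05 × 90 / 730 = 0.6% to 0.20 × 90 / 365 = 4.9%, and the observed ratio from 0.802 to 0.818.

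**Scale against precision.** At the high end of the main case, log(0.814 / 0.80) is about 0.017. The matched sample has 2 × 222,015 = 444,030 patients (Section 8). Assuming 1.00 year of counted follow-up and 15–25 events per 1,000 person-years, there would be about 6,700–11,100 events, and the standard error of the log hazard ratio, 2/√events, would be about 0.025–0.019. The shift is therefore below one standard error under these assumptions.

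**Not computed.** Leftover supply at a switch is left out. So is add-on use: no add-on rate is given, and the formula does not describe dual-use time, when the index drug is still being taken.

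**The case against.** The strongest objection is that the rule may exist in a place that cannot be read. In the readable text, analyses 1 and 3 have the same eligibility, start date, outcome definition and stopping events, so whatever separates them is probably elsewhere. Section 4 has a figure on alternate analysis approaches with a key for included and excluded person-time, and a switch rule could be drawn there. This stands as a limit on certainty. It does not remove the need for the written list, which would be programmed, to state the rule.

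Second, the 90-day grace period is deliberate, and an early event after a switch is not clearly due to the new drug. Whether to cut that window at a switch is partly a design choice. This also stands, but the choice should then be stated.

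Third, dual use looks rare at entry: the flowchart in Section 5c removes 88 of 964,801 patients for qualifying in more than one exposure category and none for concomitant use on the index date. Those counts say nothing about use during follow-up, but they give no support for assuming a large add-on share.

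A reader might also infer that a patient who adds the other group is never censored. That is not so: index-drug discontinuation plus 90 days and the other four events still apply. Only the add-on itself does not censor. Nor is add-on time comparator-only time.

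**Conclusion.** The gap is real in the readable text of analyses 1, 3 and 4, and closing it is a cheap improvement. Its size cannot be derived from the documents. Under the assumptions above, the switch tail alone moves a true hazard ratio of 0.80 to about 0.80–0.81. Add-on use would increase the misattribution by an amount that nothing in the plan allows one to state.

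Two stronger readings are tempting but not supported. One is that the error always pulls the hazard ratio toward 1. That holds only if switching is unrelated to dementia risk; if switches follow symptoms, the direction is uncertain. The other is that all four analyses are affected. Analysis 2 does not stop at discontinuation, so the point does not apply to it.

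The drug names need reconciling whatever is decided on switching. Hydrochlorothiazide appears in the discontinuation rule and in the cohort summary of Section 5a, while Sections 1a, 5b and 6a give atenolol, bisoprolol and sotalol as the comparator.

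**What to change.** 1. Add to the censoring list for analyses 1, 3 and 4: *the date of first dispensing of any drug of the other exposure group*.
2. Report the number of switches and add-ons by group, so that readers can judge the size.
3. Reconcile the drug names in the discontinuation rule and in Section 5a with the comparator in Sections 1a, 5b and 6a, and state that moves within a group do not end the episode.
4. If the design figures already show a switch rule, make the written list match them.

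The dispensing data are already needed for the discontinuation rule, so the work is one more date per patient. The cost is slightly less person-time. Censoring at a switch may itself be informative. The plan has no weighting at present, but inverse-probability-of-censoring weights could be added as a sensitivity analysis.

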- No use of Propranolol, Carvedilol and Atenolol, Bisoprolol, Sotalol concomitantly on index date
- No diagnosis of dementia any time prior to and including index date
- At least 1 inpatient claim or 2 outpatient claims with hypertension diagnosis recorded in 365 days prior to index

DREAM study protocol - Comparison 13 Propranolol or Carvedilol vs Atenolol, Bisoprolol, Sotalol

date

- 180-day continuous use of Propranolol or Carvedilol or Atenolol, Bisoprolol, Sotalol starting on the index date

c. Flowchart of the study cohort assembly

	Less Excluded Patients	Remaining Patients
All patients		27,099,355
Did not meet cohort entry criteria	-20,951,408	6,147,947
Excluded due to insufficient enrollment	-2,442,601	3,705,346
Excluded due to prior use of referent	-1,096,162	2,609,184
Excluded due to prior use of exposure	-1,644,383	964,801
Excluded because patient qualified in >1 exposure category	-88	964,713
Excluded based on Dementia Exclusion	-55,850	908,863
Excluded based on Nursing home admission	-46,478	862,385
Excluded based on Propranolol/Carvedilol OR Atenolol / Bisoprolol / Sotalol Copy	-27,923	834,462
Excluded based on Propranolol / Carvedilol AND Atenolol / Bisoprolol / Sotalol concomitantly on index date Copy	0	834,462
Excluded based on Hypertension: 1 inpatient or 2 outpatient claims within 365 days	-15,211	819,251
Excluded based on Age < 65 years	-1,914	817,337
Final cohort		817,337

6. Variables

a. Exposure-related variables:

Study drug:

The study exposure of interest is initiation of Propranolol or Carvedilol

Comparator:

Initiation of Atenolol, Bisoprolol or Sotalol

b. Covariates:

Demographics	
Age	Region
Gender	Calendar year of index date
Race	Low income subsidy
Dementia risk factors	
Diabetes	Anxiety
Obesity	Bipolar disorder
Coronary artery disease	Schizophrenia
Depression	
Markers for healthy behavior, frailty, healthcare use	
Smoking	Number of hospitalizations
Mammography	Number of physician office visits
Colonoscopy	Number of serum creatinine tests ordered
Fecal occult blood test	Composite frailty score
Influenza vaccination	Number of C-reactive protein tests ordered
Pneumococcal vaccination	Osteoporosis
Herpes zoster vaccination	Fractures

Bone mineral density test	Falls
Number of distinct generic agents	Use of supplemental oxygen
Number of emergency room visits	Combined comorbidity score
Number of outpatient visits	Number of Cardiologist visits

Comedication use	
Lithium	Nitrates

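### Analyses 1, 3 and 4 censor at drug discontinuation with no method for dependent censoring, and analysis 2 is only a partial check

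*Combined protocol and SAP*

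**What the plan says.** Section 6c gives one follow-up rule to three of the four analyses: "For analysis 1,3, and 4 the follow-up will start the day after initiation". One of the events that end follow-up is "The date of drug discontinuation, defined as the date of the last continuous treatment episode of the index drug", extended by a grace period of "90 days after the end of the last prescription's days' supply in main analyses". The parenthesis that names the index drug reads "Propranolol or Carvedilol and hydrochlorothiazide", although section 6a gives atenolol, bisoprolol or sotalol as the comparator.

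Analysis 2 is built differently. Section 5b requires "180-day continuous use of Propranolol or Carvedilol or Atenolol, Bisoprolol, Sotalol starting on the index date". Section 6c then says "For analysis 2, the follow-up will start 180 days after initiation", lists no discontinuation event, and adds the end event "Maximum allowed follow-up time (1095 days) reached".

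Section 7 controls confounding by 1:1 matching on a propensity score built from baseline covariates. Section 9 says "In the PS-matched sample, we will use cause-specific hazard models" and treats death as the competing event. It also plans hazard ratios for 1, 2 and 3 years. The text mentions no censoring weights, no covariates updated during follow-up, no report of discontinuation by arm and no sensitivity analysis for dependent censoring.

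**The concern.** Censoring at discontinuation is harmless only if, given what is adjusted for, patients who stop have the same later dementia risk as those who continue. Here that is doubtful. Early cognitive decline can plausibly change refill behaviour months before dementia is coded. Matching makes the arms alike at the index date but does not keep them alike among patients still on drug a year later. A cause-specific hazard model deals with death; for discontinuation it still assumes independent censoring.

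If the arms lose patients in early decline at different rates, the arm that loses more of them appears protected. With 222,015 patients per arm the interval is narrow, so a modest bias could be reported as a precise finding.

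**Working it through.** The plan states no power, event count, incidence, stopping rate or interval width, so there is no figure of its own to reproduce. From the documents: 222,015 patients per matched arm, the 90-day grace period, the 180-day entry condition and the 1095-day cap of analysis 2. Everything else below is an assumption.

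**Model with no drug effect.** 4% of patients are in an unrecorded prodrome at index. Others enter it at 2% per year. Prodrome leads to a dementia diagnosis at 0.4 per year. Mortality is 5% per year. Patients stop at a base rate set by arm, multiplied by *k* while in prodrome. In analyses 1, 3 and 4 a patient is censored 90 days after stopping, with follow-up of at most 5 years (the plan sets no cap there). For analysis 2, anyone who stops before day 180 is left out, follow-up starts at day 180 without discontinuation censoring, and the 1095 days are counted from day 180. The hazard ratio is the large-sample solution of the one-covariate Cox score equation.

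| Stopping per year, A v B | *k*, A v B | HR, analyses 1, 3, 4 | HR, analysis 2 |
|---|---|---|---|
| 0.5 v 0.5 | 2 v 2 | 1.00 | 1.00 |
| 0.75 v 0.5 | 1 v 1 | 1.00 | 1.00 |
| 0.6 v 0.5 | 2 v 2 | 0.958 | 0.979 |
| 0.75 v 0.5 | 2 v 2 | 0.910 | 0.950 |
| 0.5 v 0.5 | 2 v 1.5 | 0.88 | 0.947 |

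**Interval width.** The 95% half-width on the log scale is 1.96 × √(1/d_A + 1/d_B).
- Row 3: 2.10% and 2.41% have events, about 4,652 and 5,358. Half-width 1.96 × √(1/4,652 + 1/5,358) = 0.039, lower limit at HR 1 exp(−0.039) = 0.96. The bias is borderline.
- Row 4: about 3,899 and 5,358 events, half-width 0.041, lower limit 0.96. The bias is well outside.
- Row 5: about 5,358 and 6,118 events, half-width 0.037, lower limit 0.96. The bias is well outside.

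**Share of the bias left in analysis 2**, on the log scale: ln 0.979 / ln 0.958 = 0.49; ln 0.950 / ln 0.910 = 0.54; ln 0.947 / ln 0.88 = 0.43. That is roughly half. Following all initiators from day 1 regardless of stopping gives 1.00 in every row, because nothing is then selected on persistence.

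**A second model as a check.** Here a fixed binary factor raises both dementia and stopping (prevalence 5–20%, dementia rate ratio 2–5, incidence 15 per 1,000 person-years, stopping rates up to 0.7 per year). When the factor acted equally on stopping in both arms, HR was 0.965 to 1.000, and none of 45 scenarios passed the interval limit. When it acted differently by arm, 21 of 45 did. For example, prevalence 10%, rate ratio 3 and *k* 2 v 1 gave 0.943 against a limit of 0.965. A weak link (prevalence 5%, rate ratio 2, *k* 2 v 1) gave 0.983, inside the limit.

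**How far the interval itself is assumed.** For a 1:1 comparison the half-width is 1.96 × 2/√events. Incidence of 5 to 30 per 1,000 person-years and 0.5 to 3 years of mean follow-up in 444,030 patients give 1,110 to 39,960 events. At HR 1 the interval then runs from 0.889–1.125 to 0.981–1.020.

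**The case against.** The strongest reply is that bias needs two things together: stopping linked to decline, and an arm difference in the rate of stopping or in the strength of the link. Both groups are beta-blocker initiators in an active-comparator design, and nothing in the documents shows such a difference. That stands. A reader might infer that censoring produces a false effect larger than the confidence interval. The documents do not support this, because every rate behind that comparison is assumed and plausible scenarios give no bias or bias within the interval.

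Second, analysis 2 drops the discontinuation rule, so a result driven by informative stopping should shrink there. That also stands, and it would be wrong to treat analysis 2 as no check at all. But its entry condition removes early stoppers, and its population, start and cap all differ from the other analyses. A discrepancy with analysis 1 could not be put down to censoring.

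Third, the planned interval-specific hazard ratios would show drift. In the three biased scenarios they go from 0.983, 0.960 and 0.956 in year 1 to about 0.92, 0.82 and 0.78 in year 3. This is a useful diagnostic, but a cumulative drug effect would look similar, so it is not a correction.

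Finally, the design figures are not available here. They may show how analysis 3 differs from analysis 1, and the reference to main analyses suggests that other grace periods are intended. Neither changes the censoring rule written for analyses 1, 3 and 4.

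**Conclusion.** The gap is real. Three of four analyses censor at discontinuation with baseline matching only, and no analysis described in the text follows all matched initiators from day 1 regardless of stopping. The consequence is conditional. Under assumed rates the null hazard ratio lies between 1.00 and about 0.88 against a 95% half-width of about 4%, or above 1 to a similar degree if the arms are swapped. Analysis 2 retains roughly half of that bias. Whether the bias exists here, and in which direction, depends on discontinuation patterns that the plan does not undertake to report. This should be changed, but it does not show that the planned estimates are wrong.

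**What to change.** - Add an as-started analysis of the full matched cohort: follow-up from day 1, no discontinuation censoring, no 180-day requirement, capped at 1095 days.
- Report discontinuation over time by arm.
- For analyses 1, 3 and 4, report beside the unweighted hazard ratio one with stabilised inverse-probability-of-censoring weights. Fit these by arm, using the section 6b covariates updated during follow-up (for example frailty score, hospitalisations, visits, number of drugs, comorbidity score).
- Reconcile the discontinuation rule in section 6c, which names hydrochlorothiazide, with the comparator in section 6a. As written, censoring in the comparator arm is not properly defined.

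The cost is programming on data already held and a wider weighted interval. The weights correct only as far as claims covariates capture decline, and an as-started estimate dilutes a true on-treatment effect. For that reason agreement in direction should not be a condition for claiming an effect; direction says little near a hazard ratio of 1. The estimates should be shown together and differences discussed.

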Obesity	148,289 (25.4%)	50,211 (21.5%)	0.09	48,216 (21.7%)	48,375 (21.8%)	0.00
Schizophrenia	3,054 (0.5%)	1,101 (0.5%)	0.00	1,045 (0.5%)	1,064 (0.5%)	0.00
Markers for healthy behavior, frailty, healthcare use						
Bone mineral density test, n (%)	247 (0.0%)	135 (0.1%)	-0.04	141 (0.1%)	123 (0.1%)	0.00
Colonoscopy, n (%)	64,492 (11.0%)	26,148 (11.2%)	-0.01	24,751 (11.1%)	24,752 (11.1%)	0.00
Fecal occult blood test, n (%)	43,860 (7.5%)	19,665 (8.4%)	-0.03	18,342 (8.3%)	18,285 (8.2%)	0.00
Influenza vaccination, n (%)	355,785 (60.9%)	143,137 (61.3%)	-0.01	136,240 (61.4%)	136,167 (61.3%)	0.00

DREAM study protocol - Comparison 13 Propranolol or Carvedilol vs Atenolol, Bisoprolol, Sotalol

Mammography, n (%)	87,549 (15.0%)	43,295 (18.5%)	-0.09	40,715 (18.3%)	40,590 (18.3%)	0.00
Pneumococcal vaccination, n (%)	169,570 (29.0%)	55,949 (24.0%)	0.11	54,070 (24.4%)	54,269 (24.4%)	0.00
Smoking, n (%)	177,079 (30.3%)	54,670 (23.4%)	0.16	52,411 (23.6%)	52,816 (23.8%)	0.00
Number of C-reactive protein tests ordered, mean (SD)	0.21 (0.81)	0.21 (0.81)	0.00	0.21 (0.86)	0.21 (0.80)	0.00
Number of emergency room visits, mean (SD)	1.87 (3.20)	1.50 (2.71)	0.12	1.51 (3.04)	1.51 (2.69)	0.00
Number of distinct prescriptions, mean (SD)	14.66 (6.45)	13.23 (6.36)	0.22	13.44 (6.02)	13.34 (6.39)	0.02
Number of hospitalizations, mean (SD)	0.90 (1.23)	0.61 (1.02)	0.26	0.61 (1.00)	0.62 (1.03)	-0.01
Number of outpatient visits, mean (SD)	14.81 (17.01)	15.01 (18.07)	-0.01	15.04 (19.64)	14.87 (17.37)	0.01
Number of physician office visits, mean (SD)	5.43 (10.24)	5.76 (11.48)	-0.03	5.77 (12.39)	5.68 (10.95)	0.01
Number of Cardiologist visits, mean(SD)	4.28 (5.14)	3.70 (5.00)	0.11	3.66 (4.93)	3.67 (4.98)	0.00
Number of serum creatinine tests ordered, mean (SD)	4.37 (3.94)	3.85 (3.32)	0.14	3.90 (3.48)	3.88 (3.34)	0.01
Composite frailty score, mean (SD)	0.22 (0.06)	0.20 (0.06)	0.33	0.20 (0.06)	0.20 (0.06)	0.00
Falls, n (%)	29,969 (5.1%)	10,173 (4.4%)	0.03	9,818 (4.4%)	9,782 (4.4%)	0.00
Fractures, n (%)	41,635 (7.1%)	15,605 (6.7%)	0.02	14,813 (6.7%)	14,855 (6.7%)	0.00
Osteoporosis, n (%)	63,351 (10.9%)	28,996 (12.4%)	-0.05	27,367 (12.3%)	27,019 (12.2%)	0.00
Use of supplemental oxygen, n (%)	21,888 (3.7%)	5,840 (2.5%)	0.07	5,735 (2.6%)	5,696 (2.6%)	0.00
Combined comorbidity score, mean (SD)	5.66 (3.07)	4.41 (2.76)	0.43	4.48 (2.71)	4.47 (2.79)	0.00
Comedication use, n (%)						

DREAM study protocol - Comparison 13 Propranolol or Carvedilol vs Atenolol, Bisoprolol, Sotalol

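### Hospital stays and emergency visits are adjusted for only as counts, so the reported balance cannot show that matched arms are alike in time since discharge, which matters most in analyses 1, 3 and 4.

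*Combined protocol and SAP*

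**What the plan says.** - **Covariates.** Section 6b lists "Number of hospitalizations" among the healthcare-use markers, and emergency room visits in the same form. The balance table in Section 8 carries the same item as a single row, "Number of hospitalizations, mean (SD". No listed covariate gives time since discharge, the reason for a stay, or whether the drug was started on leaving hospital.
- **Window.** Section 5a requires "continuous enrollment during the baseline period of 365 days before initiation". That is stated for enrollment. The window for the hospitalization count is not given in the text, so 365 days is an inference. The design figures and Appendix A, which might state it, are not available here.
- **Score and match.** Section 7 estimates the score "conditional on baseline covariates using multivariable logistic regression" and forms 1:1 pairs on the score alone, with "a caliper of 0.025 on the natural scale of the PS". No exact match, stratum or restriction by recent discharge is described, and the subgroups in Section 9 are age, sex and cardiovascular disease.
- **Start of follow-up.** Section 6c: "For analysis 1,3, and 4 the follow-up will start the day after initiation". By contrast, "For analysis 2, the follow-up will start 180 days after initiation", and analysis 2 also requires 180 days of continuous use.
- **Outcome.** In analyses 1 to 3 one inpatient claim is sufficient. Analysis 4 needs a claim plus a prescription for a symptomatic treatment within six months of each other.

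**The concern.** Acute care goes with drug choice in the unmatched cohort: mean hospitalizations 0.90 vs 0.61 (standardized difference 0.26) and emergency visits 1.87 vs 1.50 (0.12). A count gives the same value to a stay that ended yesterday and one that ended many months ago.

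Patients just out of hospital may plausibly have a raised short-term chance of a first dementia code, for example through delirium or readmission. If one matched arm holds more of them, that early excess would be read as a drug effect in the analyses that start counting the next day. Section 7 says that conditioning on the score removes measured confounding, but this covers only what is entered. Recency can be derived from the claims and is not entered.

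**Working it through.** **1. The plan's own figures.** Standardized difference = (m1 − m2) / √((s1² + s2²)/2), with means and SDs from Section 8.
- Crude hospitalizations: (0.90 − 0.61) / √((1.23² + 1.02²)/2) = 0.29/1.130 = 0.257. Reported 0.26.
- Matched: (0.61 − 0.62) / √((1.00² + 1.03²)/2) = −0.01/1.015 = −0.0099. Reported −0.01.

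Both reproduce. The count is balanced.

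**2. How much room the count leaves for recency.** Assume the counts follow a negative binomial with r = m²/(s² − m), so P(at least one stay) = 1 − (r/(r + m))^r.
- Matched exposed: r = 0.3721/0.39 = 0.954, giving 37.6%.
- Matched comparator: r = 0.3844/0.4409 = 0.872, giving 37.4%.

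About 37% of each arm would have a stay, and their timing could differ between arms without moving the count row.

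**3. Illustrative bias.** The documents hold no discharge-timing data, so every input in this step is an assumption:
- share started within 30 days of discharge after matching: pE = 25%, pC = 20%;
- dementia hazard multiplier in those patients: h = 1.5 or 2;
- the excess lasts 6 months, and mean follow-up is 1 or 2 years, so it covers a fraction f = 0.5 or 0.25 of follow-up (simple time-averaging).

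Bias factor = (1 + pE·f·(h − 1)) / (1 + pC·f·(h − 1)).

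| h | f | Calculation | Bias |
|---|---|---|---|
| 1.5 | 0.25 | 1.03125/1.025 | 0.6% |
| 1.5 | 0.5 | 1.0625/1.05 | 1.2% |
| 2 | 0.25 | 1.0625/1.05 | 1.2% |
| 2 | 0.5 | 1.125/1.1 | 2.3% |

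The bias raises the hazard ratio if the exposed arm has more recent discharges and lowers it by about as much if the comparator has more.

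**4. Plausibility of those shares.** They imply 0.25/0.376 = 66% vs 0.20/0.374 = 53% of everyone with a stay. The recency indicator would have a standardized difference of 0.05/√((0.25×0.75 + 0.20×0.80)/2) = 0.12. A scenario with fewer recent discharges, 35% vs 25% of those with a stay, gives shares of 13.2% vs 9.3% and, over the same h and f, a bias of 0.5% to 1.8%.

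**5. Precision for comparison.** Half-width = exp(1.96·√(2/events per arm)) − 1, with 222,015 per arm (Section 8) and an assumed 15 to 30 events per 1000 person-years.
- 15 per 1000, 1 year: 3,330 events, 4.9%.
- 15 per 1000 over 2 years, or 30 per 1000 over 1 year: about 6,660 events, 3.5%.
- 30 per 1000, 2 years: 13,321 events, 2.4%.

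Taking the same mean follow-up for both, bias of 1.2% to 2.3% sits against 3.5% to 4.9% at one year, and 0.6% to 1.2% against 2.4% to 3.5% at two years.

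**6. The 1-year hazard ratio.** If all patients contribute a full first year, f = 0.5 there whatever the total follow-up, so the bias is 1.2% to 2.3%. With a 2-year mean that is about double the full-period 0.6% to 1.2%. Where patients leave before the year ends, f is larger.

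**The case against.** The strongest reply is that no imbalance has been shown. The crude gap in hospitalizations concerns unmatched patients and may largely reflect a sicker exposed group (heart failure 47.9% vs 26.1%, renal dysfunction 40.5% vs 24.4%), and those conditions are in the score and balanced after matching. So are emergency visits (1.51 vs 1.51), cardiologist visits (3.66 vs 3.67), creatinine tests (3.90 vs 3.88) and frailty, all of which may track recent acute care. This stands as a reason to expect less residual imbalance. It does not settle the matter, because none of these variables dates a discharge.

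The second reply is that the plan already has safeguards. Analysis 2 skips the first 180 days, analysis 4 has a stricter outcome, and the 1-, 2- and 3-year hazard ratios could reveal a transient early effect. This also stands. But the lag protects one analysis of four and does not itself balance recency, and analyses 1 and 3 combine next-day follow-up with the single-claim outcome.

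Three stronger readings are tempting:
- *That the matched arms do differ in recency.* The documents give no discharge-timing data. They support only that such patients can be paired.
- *That all four analyses count dementia from the next day.* Analysis 2 does not.
- *That the bias could reach 10% or more.* With 35% vs 20% and a doubled hazard throughout, 1.35/1.20 gives 12.5%. But that spreads a short-lived excess over all follow-up, and 35% would be 93% of everyone modeled as having a stay (0.35/0.376). Neither is a reasonable basis.

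**Conclusion.** The concern holds as a gap in adjustment and in the balance evidence, not as demonstrated bias. Hospital and emergency use enter only as counts, so the −0.01 on the hospitalization count does not speak to time since discharge. The exposure is greatest in analyses 1 and 3, smaller in analysis 4 because of its outcome definition, and least in analysis 2 because of its lag.

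Under the main assumptions above, the full-period hazard ratio would be off by about 0.6% to 2.3%, which is less than the assumed half-width of 2.4% to 4.9%. The 1-year hazard ratio could be off by more. Presence and direction are unknown, and the 365-day covariate window is inferred. It merits a change because the effect is plausible, would not shrink with sample size, and can be checked with data already held.

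**What to change.** Add days since last acute discharge before the index date, for example 0–30, 31–90, more than 90, and none, to Section 6b and to the propensity score. Re-match, and report these rows before and after matching in Section 8. State the covariate window in Section 6b at the same time.

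Exact matching on recent discharge, or adding principal-diagnosis groups for the last stay, is optional and needed only if imbalance remains.

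The cost is a re-run of the score and the match on claims already held, and possibly the loss of some of the 222,015 pairs; the documents do not allow that loss to be estimated.
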